# **Assessment of Efficacy**

## **Outcome Measures**

Table 4 provides a basic overview of the outcome measures, with more detail provided in in Appendix B.

Table 4. Outcome measures, instruments, and time of administration

Target group	Outcome	Measure(s)	Timing
Students	Demographics	Personal Information/Demographics	Pre only
	Depression	PHQ-9	Pre and post
	Anxiety	GAD-7	Pre and post

Help-s	Quest	ral Help-Seeking Behavior ionnaire, Actual Help-seeking viour Questionnaire	Pre and post
Service	e Purpo	se Built Service Satisfaction	Post only
Satisfa	action Quest	tionnaire for Students	

#### **Pre-test/Baseline Assessment**

During the registration process, participants will complete the online battery of questionnaires including the: Demographics questionnaire; Patient Health Questionnaire (PHQ-9); Generalised Anxiety Disorder Questionnaire (GAD-7); the General Help Seeking Behaviour Questionnaire and Actual Help-seeking Behaviour Questionnaire. This will be conducted under the supervision of a researcher and teacher/school counsellor, during class time.

#### Post-test/Final endpoint Assessment

At day 43, participants will return to the website to complete the online battery of questionnaires including the: Patient Health Questionnaire (PHQ-9); Generalised Anxiety Disorder Questionnaire (GAD-7); the General Help Seeking Behaviour Questionnaire and Actual Help-seeking Behaviour Questionnaire and the Satisfaction Questionnaire for Students Acceptability and demand measured by: The number of youth and parents who consented to the study; The number of modules completed; The number of students who reported using the online CBT programs; The number of students who completed the fortnightly check-in questionnaires;

# **Assessment of Safety**

#### **Outcomes Advisory Group**

An Outcomes Advisory Group has been established to provide specific monitoring, governance, and reporting of adverse events and trial safety. This group consists of the trial manager, the lead investigators, and the medical expert. This team meets every two weeks, and on an as-needed basis, to monitor the safety of the trial. A data safety monitoring board will not be utilised in the current study. This decision was made on the basis of two key factors:

- 1. The current study targets a non-clinical population, and does not target a high risk sample.
- 2. The research platform used in the trial has an alert system which provides timely feedback to research personnel, so that distressed participants can be identified and attended to straight away. Once identified, school counsellors will be made aware of the distressed participant, so that they may provide immediate and, if necessary, ongoing assistance. This procedure ensures the highest level of care for participants, as school counsellors are appropriately trained, familiar, accessible, and available to assist should such a scenario eventuate.

## **Duty of Care and Risk Management Protocol for Risk of Significant Harm**

The following Duty of Care and Risk Management Protocol will be used if a research participant self-identifies or self-reports as being at "risk of significant harm" during the study.

## Defining "risk of significant harm"

This document will use the definition of "risk of significant harm" as outlined in the NSW Children and Young Person (Care and Protection) Act 1998 and this definition will be applied across all schools in involved in the study. Under the act, a risk of significant harm involves serious threats to safety, welfare, and wellbeing of a child for any of the following reasons:

- The basic physical or psychological needs of the child or young person are not being met (neglect);
- The parents or caregivers have not arranged necessary medical care (unwilling or unable to do so);
- Risk of physical or sexual abuse or ill-treatment (physical or sexual abuse);
- Parent or caregiver's behaviour towards the child causes or risks psychological harm (emotional abuse);
- Incidents of domestic violence and as a consequence a child is at risk of serious physical or psychological harm (domestic or family violence).
- Students may also be at risk of harming themselves or others, such as reported suicidal thoughts/plans/behaviours, or thoughts/plans/behaviours in regards to hurting someone else.

The NSW Department of Education has established a policy titled "Protecting and Supporting Children and Young People Policy" which is enforced in all NSW schools and clearly sets out the roles and responsibilities of staff in relation to child protection including training, reporting on safety, and supporting children and young people, as well as monitoring, evaluation and reporting requirements.

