## **Type of Endpoint**

Efficacy/Safety: to measure the intervention's influence on help-seeking for depression, anxiety and stress; and to show that the intervention is safe under conditions of the proposed protocol.

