## **Inclusion Criteria**

Participants will be aged between 12 – 19 years and attending one of the participating high schools. Both males and females will be eligible. As well as including participants that are well, this trial will include adolescents with current depressive symptoms or any adolescents with a history of depression or anxiety. This trial will also include adolescents with current suicidality or a history of suicidality. Participants will be required to have an active email address for the duration of the trial as well as internet access either at home or at school (the school will provide internet access for the duration of the trial). Only those who provide signed written consent from their parents will be included.

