## Procedure for responding to risk of significant harm within this Trial

Within the Smooth Sailing service, the pre-test and post-test assessments include the Patient Health Questionnaire (PHQ-9). This questionnaire is used to assess the presence of depression symptoms and has one item assessing suicidal risk (item 9). This item reads "Over the past two weeks, have you had any thoughts that you would be better off dead or of hurting yourself in some way". A participant is able to answer either 'not at all' (0); 'several days' (1), 'more than half the days' (2) or 'nearly every day' (3). The battery also includes the General Anxiety Disorder Questionnaire (GAD-7) which is used to screen for the presence of general anxiety symptoms. Both the PHQ-9 and GAD-7 are standardised psychological screening measures and as such, may provide an objective measure of anxiety, depression, and suicide risk if completed truthfully. However, further assessment from a trained mental health professional is required for the extent of an individual's risk to be fully determined. As such, the most appropriate response to elevated scores is to notify a trained mental health professional so that they can follow up with the participant. This is a commonly accepted protocol for mental health research studies. In the context of this study, the trained mental health professional will be the School Counsellor.

Given the sensitive nature of the questionnaires, students must be provided with adequate supervision for completion. In the current study, any student participating in the trial will be subject to the following supervisory conditions:

• Students will only be able to complete the questionnaires during class time, under the supervision of the researcher, school counsellor and/or class teacher. This will ensure that the student has adequate supervision, and if an alert is triggered, the school

- counsellor will be able to make timely contact. This will also ensure that the research team will be able to monitor the impacts of this questionnaire more precisely. Any student who cannot attend school for the class period in which the baseline and follow-up questionnaires are to be completed will not be able to participate in the study.
- A trained mental health researcher from the Black Dog Institute will be present at the
  school during class time for the completion of the baseline and follow-up

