## **Summary of Potential Adverse Events**

The table below outlines a series of possible adverse events that may be captured by the assessments within this study. These events will be monitored by the number of email triggers sent by the service during the study period.

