**Table 1. Potential Adverse Events** 

Event	Assessment/Criteria	Action
"Moderately	A Patient Health	An automatic email alert will be sent to the
severe" or "severe"	Questionnaire-9 (PHQ-9)	nominated school counsellor and a member
depression at	baseline score of 15 or	of the research team. The school counsellor
baseline	above.	will be notified to follow-up with the
"Moderately	A Generalised Anxiety	participant using normal school protocols,
severe" or "severe"	Disorder (GAD-7)	including any mandatory reporting
anxiety at baseline	baseline score of 15 or	requirements. The trial manager will also re-
	above.	contact the school counsellor within 48

		hours to confirm that the email notification was received and is being acted upon. The research team will report to the outcomes advisory group at 2-week intervals on the total number of alerts.
Suicidal ideation at baseline	A score greater than or equal to one on the PHQ-9 item 9.	As above. In addition, a pop-up alert is shown to the participant which states the following: "Thanks for letting us know. We think it'd be great if you could tell a trusted adult about how you have been feeling. If you're not up to talking to someone you know, try Kids Helpline on [name] (it's not just for kids!) or Lifeline [name]. Smooth Sailing will let your School Counsellor know that it's been tough for you lately. Your School Counsellor will touch base with you in the next few days, just to see if there is anything they can do to help. Don't worry - this is all done very privately. In the meantime, keep using Smooth Sailing - we're here to help!"In addition, the participant will automatically receive access to the Smooth Sailing program which includes a range of psycho-education, help-seeking resources, and online therapy programs, which are evidence-based. Participants have access to this program for the duration of the trial.

Please see the supplementary material "Responding to risk of harm" document for a more detailed outline and flowcharts for decision making regarding risk of harm in the current trial.

Table 2 outlines additional adverse events during the trial which are not captured by the assessments and our action.

[figure not shown]

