**Table 2. Additional Adverse Events** 

Event	Assessment/Criteria	Action
Participant reports		Normal school protocols (as outlined by the
elevated suicide risk to	School Counsellor is	Protecting and Supporting Children and Young
school	notified and assessed	People Policy) are followed.
Participant reports	participant's risk	
depressed mood to	using normal school	School Counsellor to report these events to the
school	protocols.	trial manager via phone call or email.
Participant reports		
anxiety to school		The trial manager asks school counsellor about
Risk of significant harm		any adverse events upon 6 week follow-up
as identified by school		
contact		The research team will report to the Outcomes
		Advisory Group at 2-week intervals on the total
		number of trigger emails being sent.

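### No adverse event row identifies an actual suicide attempt or act of self-harm, and the safety count sent to the Outcomes Advisory Group is trigger emails only

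*Protocol*

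**What the plan says.** Under Type of Endpoint, the protocol sets itself the task "to show that the intervention is safe under conditions of the proposed protocol". Under Inclusion Criteria it states: "This trial will also include adolescents with current suicidality or a history of suicidality".

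Possible adverse events are listed in two tables under Summary of Potential Adverse Events. These are separate from the step-allocation and care tables that carry the same numbers.

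- **Adverse event Table 1** has three rows, all questionnaire results at baseline. The suicidality row is "A score greater than or equal to one on the PHQ-9 item 9". The events are tracked as follows: "These events will be monitored by the number of email triggers sent by the service during the study period".
- **Adverse event Table 2** covers events that the assessments do not pick up. It has four rows: a student telling the school of elevated suicide risk, of depressed mood, or of anxiety, and "Risk of significant harm" as identified by the school contact.

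The last term has its own definition section, to be applied in all participating schools: "a risk of significant harm involves serious threats to safety, welfare, and wellbeing of a child for any of the following reasons". The list has six entries. The sixth begins "Students may also be at risk of harming themselves or others, such as reported suicidal thoughts/plans/behaviours" and goes on to cover harming someone else.

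Under Table 2 the counsellor reports events to the trial manager by phone or email, and the trial manager asks the counsellor about adverse events at six weeks. The two-weekly report to the Outcomes Advisory Group is the total number of trigger emails.

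**The concern.** In a trial that admits currently suicidal adolescents and claims safety as an endpoint, an attempt or act of self-harm is the event a safety statement most needs to identify. The event scheme gives it no place of its own. The nearest row borrows a child-protection definition that suits deciding how a school must respond, but that puts self-harm in the same class as neglect, abuse and domestic violence. If acts are not distinguished when they are recorded, they may not be separable at analysis. The trial could then report a safety figure that carries no information on self-harm in either direction.

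**Working it through.** No arithmetic is needed for the main point. The protocol states no figure to reproduce here, and no event rate from which to project one. The check sets each event row against the definition and the reporting rule.

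**Step 1. What each row captures.**

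| Row | Basis | Identifies an act of self-harm? |
|---|---|---|
| Table 1, depression | PHQ-9 of 15 or more at baseline | No |
| Table 1, anxiety | GAD-7 of 15 or more at baseline | No |
| Table 1, suicidal ideation | PHQ-9 item 9 of 1 or more at baseline | No, thoughts only |
| Table 2, elevated suicide risk | Student tells school; counsellor assesses | No, an act could be logged here but not as an act |
| Table 2, depressed mood | Student tells school | No |
| Table 2, anxiety | Student tells school | No |
| Table 2, risk of significant harm | Six-reason definition | No, behaviour is named but merged with other reasons |

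Item 9 asks "have you had any thoughts that you would be better off dead or of hurting yourself in some way", which concerns thoughts. Rows specific to an act: 0 of 3 + 4 = 7. Rows whose definition names suicidal behaviour: 1 of 7.

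**Step 2. What the risk-of-significant-harm row contains.** The first five reasons are unmet basic needs, medical care not arranged, physical or sexual abuse, emotional abuse, and domestic violence. None concerns self-harm. The sixth combines self with others, and thoughts and plans with behaviours. An entry in this row therefore does not say which of these occurred.

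**Step 3. Overlap.** A student who tells the school of suicidal thoughts meets the sixth reason and also fits the suicide-risk row. No rule assigns the event to one of them.

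**Step 4. What is counted.** Adverse event Table 1 has the total number of alerts reported every two weeks; adverse event Table 2 has the total number of trigger emails. The emails are generated by questionnaire answers. The protocol introduces Table 2 as covering events the assessments do not capture. An attempt that comes to light through the school therefore adds nothing, as such, to the specified count. If the same student also endorses item 9 at an assessment, the resulting email records thoughts, not the act.

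**The case against.** The strongest reply is that these are response tables: each row is paired with an action, and nowhere does the protocol say that Table 2 rows will be tallied as a safety result. Classification and summary of events may sit in a statistical analysis plan, an adverse event form or the supplementary document on responding to risk of harm, none of which is shown. In a study with a recruitment target of 106, the counsellor's phone call or email has content, the six-week question is open, and the Outcomes Advisory Group includes a medical expert and meets every two weeks. A reported attempt would probably be known as an attempt.

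Much of this stands, and it rules out three stronger readings that a reader might infer.

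- That the risk-of-significant-harm row is the only one that could receive an attempt: not so, since one disclosed to the school also fits the suicide-risk row.
- That the trial could not learn of self-harm: the counsellor reports and the six-week question could reveal it.
- That a reported row count will hide attempts or count a disclosure twice: the only counts the protocol defines are alerts and trigger emails, so that would assume a tally it does not specify.

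What does not stand is that nothing needs changing. The categories are fixed in the protocol's own tables, no category exists for an act learned through the individual reports, and the specified report does not itemise Table 2 events. It is also fair to say that splitting a row achieves nothing if Table 2 events are not themselves reported; the fix has to cover both.

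**Conclusion.** The point holds as a defect in how safety events are classified and reported. None of the seven rows identifies an attempt or act of self-harm; the one row whose definition names suicidal behaviour mixes it with five unrelated reasons and with harm to others; and the specified count, trigger emails, does not show it. The protocol should be amended, because the safety endpoint cannot be answered for self-harm from the count it specifies.

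The size is structural. No numerical bias can be derived, because the documents give no event rates. The conclusion assumes that the supplementary document, described as giving detail and flowcharts for decisions about risk of harm, does not classify events for reporting. If it does, the remaining step is to bring that classification into the protocol.

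A reader might also infer that child-protection events cannot be effects of the service and may be set aside, or that safety can rest on self-harm alone. The documents support neither. The service includes counsellor contact as well as online content, and the endpoint concerns safety in general. Even a clean record would be limited evidence: with 0 events in 106 students, the exact two-sided 95% upper limit is 1 − 0.025^(1/106) ≈ 3.4%, and there is no comparator.

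**What to change.** In adverse event Table 2, replace the single risk-of-significant-harm row with three:

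- (a) actual self-harm or suicidal behaviour since registration;
- (b) harm or threat of harm to others;
- (c) child-protection concern, meaning the first five reasons in the definition.

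State that suicidal thoughts without behaviour (which should include plans not acted on) are counted only in the existing suicide-risk row, and that each event falls in one row. Report the number of students with each Table 2 event, out of those registered, to the Outcomes Advisory Group and in the safety results, alongside the trigger-email count. Make no prior statement on causality for any category. The school's response procedure stays as it is; only recording and reporting change.

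The cost is one extra category field when the counsellor reports an event, and a short table in the two-weekly report.

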## Procedure for responding to risk of significant harm within this Trial

Within the Smooth Sailing service, the pre-test and post-test assessments include the Patient Health Questionnaire (PHQ-9). This questionnaire is used to assess the presence of depression symptoms and has one item assessing suicidal risk (item 9). This item reads "Over the past two weeks, have you had any thoughts that you would be better off dead or of hurting yourself in some way". A participant is able to answer either 'not at all' (0); 'several days' (1), 'more than half the days' (2) or 'nearly every day' (3). The battery also includes the General Anxiety Disorder Questionnaire (GAD-7) which is used to screen for the presence of general anxiety symptoms. Both the PHQ-9 and GAD-7 are standardised psychological screening measures and as such, may provide an objective measure of anxiety, depression, and suicide risk if completed truthfully. However, further assessment from a trained mental health professional is required for the extent of an individual's risk to be fully determined. As such, the most appropriate response to elevated scores is to notify a trained mental health professional so that they can follow up with the participant. This is a commonly accepted protocol for mental health research studies. In the context of this study, the trained mental health professional will be the School Counsellor.

Given the sensitive nature of the questionnaires, students must be provided with adequate supervision for completion. In the current study, any student participating in the trial will be subject to the following supervisory conditions:

• Students will only be able to complete the questionnaires during class time, under the supervision of the researcher, school counsellor and/or class teacher. This will ensure that the student has adequate supervision, and if an alert is triggered, the school

- counsellor will be able to make timely contact. This will also ensure that the research team will be able to monitor the impacts of this questionnaire more precisely. Any student who cannot attend school for the class period in which the baseline and follow-up questionnaires are to be completed will not be able to participate in the study.
- A trained mental health researcher from the Black Dog Institute will be present at the
  school during class time for the completion of the baseline and follow-up
  questionnaires. This researcher will supervise students during their completion of the
  questions, and monitor for distress. This researcher will verbally explain the process
  and provide instructions for what a student should do if feeling distressed (a. Let the
  researcher or the teacher know immediately by putting their hand up or asking to be
  excused). This researcher will have a valid WWCC which is included in the application.
- The school counsellor will also be onsite at the school and available for immediate contact for any students who require this during the completion of the baseline and follow-up questionnaires.
- A private breakout space (i.e. a classroom or school counsellor's office) will be made available should any student require private support.
- If a student reports that they are moderately severe or severely depressed/anxious during the baseline or follow-up questionnaires, then the school counsellor will be notified using the procedures outlined below under "Procedure for Responding to Risk of Significant Harm". The trial manager will also be notified and will follow-up with the school counsellor within 48 hours to ensure that the school counsellor is responding to the alert. Please note that the Trial Manager will be onsite for the completion of the baseline and follow-up questionnaires, and will therefore be able to check notifications immediately while participants are in the room. This allows for a swift response.
- To further support the school counsellor, a list of resources will be provided to the before the study commences, outlining additional adolescent mental health services that are available in their local area for referral. The Smooth Sailing Clinical Advisory Group (which consists of Child and Adolescent Psychiatrist and a Clinical Psychologist located at the Black Dog Institute) will also be available to provide any clinical support to the school counsellors wherever it is requested via telephone and email. This will ensure that the school counsellor feels adequately supported throughout the study, and increases the clinical capacity available to the students.

